- 9 The four sites, each of which will be treated as a cluster in the analysis, are Alberta Children's Hospital and South Health Campus in Calgary (treated as a single site because they are staffed by the same group of pediatric physicians), and Stollery Children's Hospital, North East Community Health Center, and Grey Nun's Hospital in Edmonton (each of these Edmonton sites is staffed by different physician groups and will therefore be treated separately). The sites were selected because they represent high-volume centres that account for a significant proportion of children diagnosed with concussion in acute care settings in Alberta. Collectively, they accounted for 2,098 concussion diagnoses over 12 months in 2015-2016, as well as another 1,517 cases with the diagnosis of head injury, unspecified, which is often used in place of the more specific diagnostic code (see Table 1 on next page). Our project team includes the emergency medicine physicians who are the academic and clinical leaders for emergency medicine in both Calgary ([name]) and Edmonton ([name]).

All four clinical sites have provided enthusiastic letters of support for the proposed project, and will allocate staff time and provide space for project activities as in-kind contributions. More specifically, the operational leads at the sites have agreed to encourage the participation of their physicians and nurses in the project and to provide space needed for project site visits, key informant interviews, and staff training. The participation of the PI, Co-PIs, and all Co-Investigators is strongly supported by their respective academic institutions.

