Secondary outcomes also will include measures of physician adherence, the number of unique website hits per IP address, the proportion of patient- and parent-reported adherence to physician discharge recommendations, the proportion of diagnosed concussions per visit (predicted to increase as physicians identify and code the injuries correctly), and the proportion of CT scans ordered per diagnosed concussion (predicted to decrease because the CP will include prediction rules for CT scanning in concussion).

12c *Table 3: Process and clinical outcomes*

| Outcome measure      | Description         | Details  |
|-----------------------------|----------------------------|---|
| Primary clinical outcome    | Time to symptom resolution | Weekly ratings by patients and parents of whether patient has returned to pre-injury status   |
| Secondary clinical outcomes | Postconcussive symptoms    | Weekly ratings on Health and Behaviour Inventory  |
|                             | Quality of life            | Weekly ratings on PedsQL  |
|                             | Satisfaction with care     | Post-visit rating of overall satisfaction with acute care   |
| Primary process outcome     | Physician adherence        | Proportion of completed discharge forms per diagnosed concussion    |
| Secondary process outcomes  | Patient/parent adherence   | Proportion of patient and parent reports of adherence to physician discharge recommendations involving rest, return to school, and return to play |
|                             | Patient/parent adherence   | Number of unique website hits per IP address  |
|                             | Physician adherence        | Proportion of diagnosed concussions per visit   |
|                             | Physician adherence        | Proportion of CT scans ordered per diagnosed concussion   |

Qualitative interviews and site surveys resulted in the discharge form being replaced by the 5P risk score sticker. To assess adherence, the study team recorded the number of 5P assessments completed by each site over the course of data collection.

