17b The web portal will send email reminders to participating families to complete serial symptom inventories. No contact will be made by the study team unless families reach out voluntarily. Ideally, symptom data will be collected until participants fully recover, however, participants can stop entering data, or leave the study at any time.

Data management 18 The study team will not directly access AHS databases or systems. Administrative data will be accessed externally by an AHS MyChild analyst. The variables collected will be obtained for all children diagnosed with concussion at any of the participating AHS facilities during the conduct of the stepped wedge clinical trial. The data will be de-identified, except for children whose parents have consented to linkage of web portal responses with health records. Individual data entered through the web portal by parents and children will download into the secure REDCap database. The database servers will be located under Canadian jurisdiction and be administered by the Clinical Research Unit of the University of Calgary. These servers are part of the CRU infrastructure and maintained in accordance with strict security and privacy controls.

Results from the project will be reported in aggregate format. If individual materials are presented, all personal identifiers will be removed. These safeguards should maintain confidentiality and minimize any risks associated with participation in the project.

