Statistical methods 19a Statistical analyses will involve comparisons of primary and secondary outcomes prior to versus after CP implementation. Children will fall into either the pre-CP or post-CP group because their care (including the version of the website and text messaging they receive) will be based strictly on when they present for acute care (i.e., prior to or after CP implementation at their respective site). Time to symptom resolution will be the primary outcome, and will be examined using survival analyses. First, Kaplan Meier estimates of the curves will be created, to obtain crude comparisons; Cox proportional hazards models will then be used to adjust for other variables. Apart from reporting hazard ratios, we also will present median time to symptom resolution (if reached) for pre- versus post-CP implementation. Other outcomes will be examined using mixed models with random effects for cluster, to adjust for clustering by site, and fixed effects for the test of CP status (pre/post implementation). Linear models will be used for continuous outcomes, Poisson for counts, and logistic regression models for binary outcomes. Exploratory analyses will examine whether the impact of implementation changes as sites gain more experience with the CP, by including the amount of time since the CP was implemented as a fixed effect in the model. Similarly, heterogeneity in intervention effects will be explored using testing interactions of CP status (pre/post) with site.

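### HBI and PedsQL are weekly ratings of the same child, but the model stated for them has no child-level term, no week and no single analysed value, so entering the weekly ratings gives a wrong standard error for the CP effect

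*Protocol*

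**What the plan says.** Protocol item 12c, Table 3, lists three secondary clinical outcomes. Two are repeated: "Weekly ratings on Health and Behaviour Inventory" and "Weekly ratings on PedsQL". The third, satisfaction with care, is taken once: "Post-visit rating of overall satisfaction with acute care". Item 17b confirms the repetition: "The web portal will send email reminders to participating families to complete serial symptom inventories". It also makes the number of ratings vary by family: "Ideally, symptom data will be collected until participants fully recover, however, participants can stop entering data, or leave the study at any time".

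Item 19a gives a single analysis for everything other than time to symptom resolution: "Other outcomes will be examined using mixed models with random effects for cluster, to adjust for clustering by site". The fixed effect is CP status, before or after implementation, and continuous outcomes get the linear version. The cluster is the hospital site (item 9): "The four sites, each of which will be treated as a cluster in the analysis". CP status does not change within a child (item 19a): "Children will fall into either the pre-CP or post-CP group".

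The only further terms in item 19a are exploratory: time since the CP was implemented, and CP by site. Neither concerns repeated ratings of one child.

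**The concern.** The stated model suits satisfaction with care, where each child has one value. It does not suit the two weekly outcomes beside it in Table 3. A random intercept for site absorbs differences between sites. Given site, it treats four ratings from one child as four independent observations. Because each child is wholly before or wholly after implementation, the CP effect is a comparison between children, and its precision depends mainly on the number of children, not the number of ratings.

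At stake is the standard error, and so the significance test and confidence interval, for the CP effect on symptoms and on quality of life. These are two of the trial's four patient-centred outcomes. A second matter is what the contrast means. With no week in the model and families free to stop at recovery or at any time, a pooled contrast can compare different post-injury weeks in the two groups.

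**Working it through.** **The plan's own figure.** There is none on this point. The only power calculation (item 14) is for the primary outcome.

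**Inputs from the protocol.** Ratings are weekly (Table 3). The assumed median time to resolution is 4 weeks and follow-up is 3 months (item 14). Symptoms are described as worst acutely (item 6a), so a decline over the weeks is to be expected.

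**Inputs assumed, because the protocol gives none.**
- Ratings per child, m: 2, 4 or 12. Four is weekly rating up to the 4-week median; 12 is roughly weekly rating through 3 months.
- Correlation between two ratings of one child, given week, rho: 0.3 to 0.7.
- Share of the pooled rating variance due to week since injury, v: 0 to 0.4.

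**Formula.** Suppose each child gives m ratings over the same weeks. Let s² be the variance of a rating given site and week.
- True variance of a child's mean, for comparing children: s²(1 + (m−1)rho)/m.
- Variance the stated model uses: it has no week term, so week differences fall into the residual, giving [s²/(1−v)]/m.
- Ratio of true to used variance: D = (1 + (m−1)rho)(1−v).
- The standard error is too small by the factor √D when D exceeds 1, and too large when D is below 1.
- Actual two-sided error of a nominal 5% test: 2[1 − Φ(1.96/√D)].

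**Two cells in full.**
- m = 4, rho = 0.5, v = 0: D = 1 + 3 × 0.5 = 2.5; √D = 1.58; 1.96/1.58 = 1.24; error 21.5%.
- m = 2, rho = 0.3, v = 0.4: D = 1.3 × 0.6 = 0.78; √D = 0.88; 1.96/0.88 = 2.22; error 2.6%.

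**Results for rho = 0.3 / 0.5 / 0.7.**

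| m | v | D | √D | Actual error, % |
|---|---|---|---|---|
| 2 | 0 | 1.30 / 1.50 / 1.70 | 1.14 / 1.22 / 1.30 | 8.6 / 11.0 / 13.3 |
| 2 | 0.4 | 0.78 / 0.90 / 1.02 | 0.88 / 0.95 / 1.01 | 2.6 / 3.9 / 5.2 |
| 4 | 0 | 1.90 / 2.50 / 3.10 | 1.38 / 1.58 / 1.76 | 15.5 / 21.5 / 26.6 |
| 4 | 0.4 | 1.14 / 1.50 / 1.86 | 1.07 / 1.22 / 1.36 | 6.6 / 11.0 / 15.1 |
| 12 | 0 | 4.30 / 6.50 / 8.70 | 2.07 / 2.55 / 2.95 | 34.5 / 44.2 / 50.6 |
| 12 | 0.4 | 2.58 / 3.90 / 5.22 | 1.61 / 1.97 / 2.28 | 22.2 / 32.1 / 39.1 |

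**Check by simulation.** Null data were simulated for a four-site stepped wedge and fitted with the stated model (site random intercept, CP fixed effect, restricted maximum likelihood). Site shares and between-site variance were assumed.
- No week trend, 800 children: 17.5 / 21.4 / 26.6% at m = 4 and 35.1 / 43.5 / 52.1% at m = 12.
- No week trend, up to 12 ratings but stopping at recovery: 27.1 / 36.3 / 41.0%.
- No week trend, 875 children (2,100 × 50% × 10/12) or the protocol's 1,575: 16% to 26% at m = 4 for both sizes, so more children do not cure it.
- Week share 0.4, 875 children: 2% to 5% at m = 2 and 7% to 16% at m = 4.
- One value per child (the mean of that child's ratings) in the stated model: about 5% to 8%.

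**Check of the longitudinal alternative.** With site and child random intercepts, week and CP by week, and CP averaged over equally weighted weeks, rejection was 4.5% to 7.0% in 18 settings with 2 to 4 ratings and no week trend. The mean standard error was 1.13 to 1.74 times that of the stated model.

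**The case against.** The strongest reply is that item 19a does not commit the trial to this error. It is one general sentence covering continuous, count and binary outcomes. Its random effect has a stated purpose, clustering by site, and nothing says that the listed terms are the only ones. Table 3 fixes how often ratings are collected, not which values are analysed. The analysis week and the within-child covariance are details that a SAP commonly supplies, and the SAP is not at hand.

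Part of this stands. A reader might infer that the protocol says all weekly ratings go into the site-only model; it does not, and with one value per child the stated model is adequate on this point. The finding is therefore conditional.

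It does not remove the point. The protocol is not silent: it names the random effect, the fixed effect and the model family, and that structure does not match two outcomes that the same protocol defines as weekly. No week or summary is named that would make it match. A SAP that follows the text with the weekly ratings inherits the error.

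A second objection concerns direction. A reader might infer that the standard error is bound to be too small. That holds only if symptoms show no trend over weeks. Where they decline, leaving week out inflates the residual variance and offsets part of the error. At 2 ratings the offset can be complete or more than complete; over the ranges examined, inflation remains at 4 and at 12. This objection is accepted and is built into the table.

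Third, the mixing of post-injury weeks cannot be given a size or a direction from the document. It is a reason to name the weeks, not evidence of bias.

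**Conclusion.** The model stated in item 19a does not fit the HBI and PedsQL as Table 3 defines them. If the weekly ratings are entered as they stand, within-child correlation is ignored for a between-child contrast and the standard error of the CP effect is wrong, usually too small. For rho 0.3 to 0.7 and v 0 to 0.4, the actual error of a nominal 5% test is about 7% to 27% with 4 ratings per child, 22% to 51% with 12, and 3% to 13% with 2.

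These ranges illustrate and do not bound the error, because m, rho and v are all assumed. The formula also takes complete ratings over the same weeks, which families who stop early will not provide.

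A reader might also infer that the trial's main result is compromised. It is not on this ground: the primary outcome has one event time per child and its own Cox analysis. Two secondary outcomes are affected, and wording settles the matter before any data are analysed.

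**What to change.** In item 19a, give HBI and PedsQL their own sentence and choose one of two routes.

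1. **Longitudinal model.** To the site and CP terms add a child-level random effect nested in site (or a within-child covariance) and week since injury with its CP interaction. Test CP at one pre-named week, or as an average over pre-named weeks.
2. **Single week.** Name one post-injury week as the analysed value and keep the stated model.

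The stated model can stay as it is for satisfaction with care. Neither route deals with other features of the model, such as calendar time.

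**Cost.** No new data are needed. Item 26 already gives each portal participant an identification number, so ratings can be grouped by child. The price is usually wider, correct confidence intervals and slightly more analysis work. The longitudinal route relies on stopping being explained by ratings already given. The single-week route sets aside the ratings from other weeks.

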## Introduction

Background and rationale

6a

Pediatric concussion is a significant public health burden, sometimes referred to as a silent epidemic. More than a million children in North America sustain a concussion annually, and the numbers seeking medical care are rising dramatically. Children with concussion often report postconcussive symptoms, including somatic (e.g., headache, dizziness), cognitive (e.g., inattention, forgetfulness), and affective (e.g., irritability, dysphoria) complaints. Postconcussive symptoms are most severe acutely, but can persist for weeks to months and result in functional disability and declines in quality of life in 15-25% of children with concussion.

Multiple evidence-based clinical practice guidelines (CPGs) have been developed to guide the management of concussion in children. However, the implementation of CPGs in clinical settings is spotty, resulting in significant practice variation and knowledge gaps. For instance, among 577 front-line primary care providers in Ontario (i.e., family physicians, emergency medicine physicians, general pediatricians, nurse practitioners, and physician assistants) who diagnose and manage concussion, only 47% recommended an initial period of school absence, only 37% correctly applied return-to-play guidelines, and only 26% reported regular use of standardized rating scales for assessing concussion. Even among emergency medicine physicians from academic medical centers belonging to the Pediatric Emergency Research Canada network, only 64% correctly applied return-to-play guidelines, 60% recommended school absence, and 22% reported regular use of standardized rating scales for assessing concussion.

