Health care utilization and costs associated with care of concussion will be compared before and after the implementation of the CP. Utilization and costs are expected to remain stable or decline following implementation of the CP.

*Overview.* The project will involve a stepped wedge cluster randomised trial to evaluate the implementation of the MNCY CP for the acute care of pediatric concussion. Stepped wedge designs randomise the sequence in which participating sites receive the study intervention, so that each site serves as its own control, but each site starts the intervention at a different time. Data collection continues throughout, so that each site contributes observations during both pre-intervention and post-intervention periods. In this case, each of four participating sites will be considered clusters, and they will be randomised to implement the MNCY CP over 11 months (i.e., after a 2 month lead-in period, implementation will occur at one site and then at the other three sites every 2 months, until implementation has occurred at all four sites, with data continuing to be collected 2 months after the CP is implemented at all sites).

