12d *Health care utilization.* We will assess the impact of the implementation of the CP on health care utilization using data from the National Ambulatory Care Reporting System (NACRS). Relevant outcomes will include acute care length of stay and return visits within 72 hours following acute care discharge. Appropriate procedures will be used to link administrative and health data. Use of NACRS data allows efficient capture of return visits, regardless of whether the patient returns to the index site. We will also use administrative data from AHS to assess health care utilization for pediatric patients with concussion. For each concussion diagnosed at the target sites, we will track the duration of stay in the ED, number of subsequent outpatient visits, and number of referrals to other health care services.

*Healthcare costs.* Payer costs associated with acute care for pediatric patients with concussion will be accounted for, based on ED visits, return visits, and physician fees, as well as subsequent outpatient care, which will be determined from the AHS administrative database. Costs for ED visits will be based on standard methodologies using resource intensity weightings (RIWs). Physician fees associated with ED and outpatient visits, including those for laboratory and diagnostic imaging services, will be captured through associated AHS billings. Cost data will be presented in Canadian dollars for the standard price year of 2014.

Participant timeline 13a *Project phases.* As shown in the Project Timeline below, the project will be divided into four phases. During the pre-implementation phase, which will last 12 months, we will complete site visits and key informant interviews, develop the intervention strategy, seek site approvals for the planned intervention, conduct a launch meeting, and complete randomization. The implementation phase will take place over the next 10 months. According to the stepped wedge design, data collection will occur continuously from 2 months prior to implementation at any site until 2 months after the CP is implemented at all four sites. Data collection will include the monitoring of outcomes, which are described below, during the course of the stepped wedge trial, which will last about 10 months.

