*Power calculation.* Power calculations for the primary outcome, time to symptom resolution, were computed using standard methods for two-group survival analyses (i.e., children who received care before versus after implementation of the CP). We conservatively assumed a sample size of 1,575, based on a total of 2,100 concussions per year across sites, a 50% rate of web site usage, and 18 months of recruitment. If we assume equal numbers of cases in the pre- and post-implementation phases, a median time to symptom resolution of 4 weeks, non-informative censoring because follow up will continue for 3 months, and no clustering effects, then the minimum hazard ratio that we can detect with .80 power at a significance level of .05 would be 1.20, which would represent at 20% higher likelihood of symptom resolution at any given time post-injury after implementation of the CP. Analyses will treat the randomised crossover from control to intervention as having occurred at the planned time, irrespective of any delays in actual implementation of the intervention, although secondary analyses will explore the effects of the actual timing of the crossover should any delays occur. All sites have provided written commitment to the study. Therefore, barring exceptional circumstances, no sites will be lost to follow-up.

Randomization

15

A study statistician will use a computerized algorithm to select a randomly generated order of implementation for the four sites.

Recruitment 16 Recruitment will rely on ongoing support and communication with clinicians. To avoid having implementation become stalled or displaced by other priorities, we will conduct monthly teleconferences with site champions to discuss progress and sustainability. Teleconferences will allow sites to discuss best practices and local solutions to common barriers. Additionally, the study coordinator and PI will be available for more informal consultation by email or phone.

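### The mixed models written out in item 19a have no calendar-period term, so in this stepped wedge the pathway effect is confounded with time; the primary Cox model is too, unless period is among its unnamed covariates

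*Protocol*

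**What the plan says.** - **Design.** The overview in the Introduction sets a four-site stepped wedge in which "after a 2 month lead-in period, implementation will occur at one site and then at the other three sites every 2 months". Item 13a says "data collection will occur continuously from 2 months prior to implementation at any site until 2 months after the CP is implemented" at all sites, about 10 months. That makes five 2-month periods, with one site crossing at the start of each of periods 2 to 5.
- **Non-primary outcomes (item 19a).** These use linear, Poisson or logistic mixed models with "random effects for cluster, to adjust for clustering by site, and fixed effects for the test of CP status (pre/post implementation"). Each term is given with its purpose. No calendar-time term appears here or elsewhere in the protocol.
- **Primary outcome (item 19a).** After Kaplan-Meier curves, "Cox proportional hazards models will then be used to adjust for other variables". The variables are not named.
- **The only time term.** Exploratory analyses ask whether the effect changes with experience, "by including the amount of time since the CP was implemented as a fixed effect in the model". This is time on the pathway, not calendar time.
- **Power (item 14).** The calculation uses "two-group survival analyses (i.e., children who received care before versus after implementation of the CP"), with a minimum detectable hazard ratio of 1.20 at N = 1,575.
- **Time and coding.** The background says "the numbers seeking medical care are rising dramatically". The secondary outcomes include "the proportion of diagnosed concussions per visit (predicted to increase as physicians identify and code the injuries correctly").

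**The concern.** Randomising the crossover order protects against a common time trend only if the model contains time. Without a time term, the CP coefficient compares earlier children with later ones, and whatever changed over the year for other reasons is added to the pathway effect.

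The outcome most exposed is diagnosed concussions per visit. A rise that would have occurred anyway, from more care-seeking or a general shift in coding, would be read as better physician adherence. For symptoms, quality of life and satisfaction, a trend could be credited to the pathway or could hide a real benefit. The primary hazard ratio carries the same risk if period is not one of the Cox covariates.

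**Working it through.** **1. The plan's own figure.** N = 2,100 × 0.50 × 1.5 years = 1,575, which reproduces. A hazard ratio (HR) of 1.20 at 0.80 power, two-sided 0.05 (sidedness assumed), needs 4 × 2.80² / (ln 1.20)² ≈ 945 events, or 60% of 1,575. With a 4-week median and 13 weeks of follow-up, the event share is 1 − exp(−(ln 2/4) × 13) = 0.895, about 1,410 events. The standard error (SE) is 2/√1,410 = 0.0533, and the minimum HR is exp(2.80 × 0.0533) = 1.16. So 1.20 does not reproduce, but it errs on the cautious side and the present point does not depend on it.

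**2. How far CP status tracks time** (equal sites, even accrual).
- Share of sites on the CP by period: 0, 0.25, 0.50, 0.75, 1.
- Mean period, pre: (4×1 + 3×2 + 2×3 + 1×4)/10 = 2.0. Post: (1×2 + 2×3 + 3×4 + 4×5)/10 = 4.0. Gap: 2.0 steps, or 4 months.
- Within a site that crosses after k periods: (k+6)/2 − (k+1)/2 = 2.5 steps.
- Under one uneven pattern (relative accrual 1.3, 1.1, 0.7, 0.8, 1.1 by period), the gap is 2.3 overall and 2.5 to 2.8 within site.

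A common trend of d per step therefore biases the CP effect by 2.0d with no site term and by 2.5d with fixed sites. With a random site effect at N = 875, generalised least squares gives 2.0d, 2.32d, 2.45d and 2.48d at intraclass correlations (ICC) of 0, 0.01, 0.05 and 0.1.

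**3. The exploratory term.** With CP status, time since implementation and fixed site effects, a trend of d leaves about 1.0d to 1.8d in the CP coefficient, depending on how that time is coded. A further 0.88d per step goes into the experience slope, where it would look like learning.

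**4. Illustrative size** (10 months, no CP effect, all drifts assumed). Diagnoses: 2,100 × 10/12 = 1,750. Portal users: 1,750 × 0.50 = 875. Visits, from the site descriptions in item 9: (77,000 + 15,000 + 50,000 + 18,000) × 10/12 = 133,333, so about 1.3% of visits are diagnosed concussions.

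| Model | Drift per step | Spurious effect | False positives |
|---|---|---|---|
| Logistic, diagnoses per visit | 1% | ratio 1.02 | 7% |
| | 2.5% | 1.05 to 1.06 | 18% to 21% |
| | 5% | 1.10 to 1.13 | 53% to 62% |
| Linear mixed, N = 875, ICC 0 to 0.1 | 0.025 SD | 0.05 to 0.06 SD | 12% to 14% |
| | 0.05 SD | 0.10 to 0.12 SD | 32% to 41% |
| Cox, CP status alone, N = 875 (1,575) | 1% | HR 1.02 | 6% (7%) |
| | 2.5% | HR 1.05 | 11% (15%) |
| | 5% | HR 1.10 | 28% (45%) |

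The logistic rows use SE 0.048 (no site variance) and 0.054 (fixed sites) on the log odds ratio. The Cox rows use HR = (1+d)² and SE 0.0715 (0.0533). For example, at 5% and N = 875: 2 ln 1.05 / 0.0715 = 0.0976/0.0715 = 1.36, which is rejected 28% of the time.

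Simulations of 1,500 runs agree. The logistic model gives 19% and 54% (CP only) or 22% and 62% (with fixed sites) at drifts of 2.5% and 5%, and 6% and 5% once periods are added. The linear mixed model gives 14% to 16% and 38% to 40% at ICC 0.01 and 0.05. It falls to 5% to 8% with periods, against 7% to 8% with no drift at all.

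**5. Price of the correction.** The variance of CP status is 0.25 unadjusted, 0.20 given site, and 0.075 given site and period. Information kept is 0.075/0.25 = 30% of the plain two-group comparison, or 0.075/0.20 = 37.5% of a model that already has fixed site effects. For Cox:
- N = 1,575: SE = 0.0533/√0.30 = 0.0973; minimum HR exp(2.80 × 0.0973) = 1.31; power at HR 1.20 is 0.47.
- N = 875: SE = 0.0715/√0.30 = 0.1305; minimum HR exp(2.80 × 0.1305) = 1.44; power at HR 1.20 is 0.29.

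**The case against.** - **The Cox covariate list is open.** Naming covariates is ordinary analysis-plan content, and that plan is not at hand. This stands, and is why the Cox point is conditional. The two-group power calculation shows how N was justified, not which covariates will be fitted.
- **The mixed-model sentence does not say its terms are the only ones.** True, but it lists each term with its purpose, in a section that elsewhere thought to add time on the pathway. A statistician who followed it would fit the biased model.
- **No trend in the outcomes is documented.** This largely stands. The background statement is about care-seeking numbers in general. It gives a direction without a rate, and says nothing about recovery time, symptoms, quality of life or CT use at these sites. With no trend there is no bias.
- **The larger drifts are steep.** Over six 2-month steps, 1%, 2.5% and 5% compound to about 6%, 16% and 34% a year. At 1%, false positives stay near nominal. However, item 9 counts 1,517 unspecified head injuries beside 2,098 concussions and says the unspecified code often stands in for the specific one, so a coding shift of some percent per step is not far-fetched for the diagnosis outcome.
- **Calendar time and time since implementation can be separated across sites.** Correct, but only if period is in the model. Within one site after crossover they move one-for-one.
- **The linear illustration uses one value per child**, whereas the scales are rated weekly. This affects the false-positive rates, not the 2.0 to 2.5 multiplier.

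**Conclusion.** The point holds. For the non-primary outcomes, the model as written leaves the CP effect biased by 2.0 to 2.5 times any common per-step trend, and neither the site effect nor the exploratory time term repairs this. For the primary outcome the same follows only if period is not among the Cox covariates. Confounding is partial: period effects are estimable here, so the fault can be corrected at a known cost in precision.

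The multiplier rests on five 2-month periods, equal sites, even accrual and a linear trend. The false-positive rates rest on assumed drifts, because the protocol quantifies none. This should be corrected before analysis: it removes the protection that randomising the crossover order was meant to give.

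**What to change.** In item 19a:
- Add fixed effects for the 2-month calendar periods of the step schedule to every linear, Poisson and logistic mixed model, including the exploratory time-since-implementation model.
- Name the same period terms among the Cox covariates, and state that the Cox model is stratified by, or adjusted for, site. Item 9 already says sites are clusters in the analysis.
- State as a limitation that period terms do not absorb changes over time specific to one site.

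In item 14, restate the detectable HR for that model, after reconciling the trial length: about 10 months in item 13a, 11 in the overview and 18 in the power calculation.

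The text change is one or two sentences, but the loss of stated power is real: 1.20 becomes about 1.31 (N = 1,575) or 1.44 (N = 875). A single linear time term saves nothing with equal sites (also 30%), because the share of sites on the CP rises by one quarter each period. Weighting sites by the emergency department volumes in item 9 (92,000, 50,000, 9,000 and 9,000, splitting the combined 18,000 evenly by assumption), period effects keep 20% to 25% of the information across all 24 crossover orders, and a linear term keeps 26% to 32%.
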